**Table 5–1: Number of decimal places for summary statistics**

Statistic	Number of digits
Minimum, maximum	Same as original data or maximum 3 decimal points
Mean, median	1 more than in original data
SD	1 more than in original data
Frequencies (%)	1 digit
p-values	4 digits

#### 5.1.1 Handling of Missing Data

This section describes the general handling of missing data that would be meaningful for the analysis in terms of the study objectives but were not collected. The rules for handling the data that do not exist or are not considered meaningful for the analysis because of an intercurrent event are described in [Section 5.3.1](#) and [5.3.3](#). No imputation of missing assessments will be performed for the secondary and exploratory endpoints unless it is specified otherwise.

All missing or partial data will be presented in the subject data listing as they are recorded on the Case Report Form (CRF) or electronic diary (eDiary).

For the computation of durations, i.e., time between start and end date of certain events and concomitant medication intake, a complete date is necessary. The following rule will be applied to impute the missing start or end date of adverse events (AE) / concomitant medications (CM):

An imputation range will be defined as the earliest possible date (lower range) and the latest possible date (upper range) of the occurrence of AE/CM. If AE/CM end date is available, this will be used as the latest possible AE/CM occurrence date in the imputation range.

The partially missing AE/CM start date will be imputed to the earliest date of the imputation range. Completely missing start date will not be imputed.

Partially missing AE/CM end date will be imputed as the latest possible date of AE/CM imputation range. Completely missing end date will not be imputed and presumed to be ongoing.

The date of permanent discontinuation of study medication will be collected in eCRF. In case of missing date, it will be determined based on last medication intake date before the discontinuation using available eDiary-data.

Unless specified otherwise, participants with missing baseline assessments will be excluded from all analyses that require the respective baseline assessment.

### 5.1.1.1 Electronic Participant-Reported Outcomes (ePROs)

There are two types of missing data for ePRO measures: missing data at the ‘form’ level and missing data at the ‘item’ level. Form level missing refers to a respondent missing an entire PRO assessment for a given time point (e.g. a given day (i.e. morning and evening eDiary) for the HFDD and a given week for the PROMIS SD SF 8b). In general, form level data may be missing due to participant’s early withdrawal from the study, inability to evaluate an endpoint at a particular time point, or non-compliance. By design of the eDiary, there will be no item level missing data for the respective ePRO questionnaires per se in so far that respondents have to select an answer for an item in order to move on to the next item on the eDiary/electronic hand-held device. This does however not apply to the MENQOL (see below).

#### 5.1.1.1.1 Hot Flash Daily Diary (HFDD)

Participants’ assessments of HF will be recorded electronically twice daily using the sponsor developed HFDD.

A diary day for the calculation of the frequency and severity of HF consists of the evening entry (Evening Hot Flash eDiary), and the morning entry (Morning Hot Flash eDiary), of the subsequent day. A day will be considered available for the calculation of the frequency and severity of HF, if at least the evening or the morning entry (of the subsequent day) is not missing. The daily number of hot flashes will be calculated as the sum of hot flashes documented in both the evening and morning diary. Retrospective data entry is possible for a limited time. For the morning diary these retrospective entries will be allowed on the same day between 11:00AM and 11:59PM. For the evening diary the retrospective entry option will be available between midnight until 10:59AM on the day after the missed entry. If only the evening or morning entry is available, then this will be used for that particular day.

For the evaluation of the frequency and severity of HF, the daily HF assessments will be aggregated to a mean daily frequency and a mean daily severity HF score from the data of a particular week (see Section 5.1.2.1). In case data is missing for more than 2 days within a week, the value for that particular week will be set to missing. Further details regarding imputation rules in case of missing week values are described in Section 5.3.1.

### 5.1.1.1.2 Patient-reported Outcomes Measurement Information System Sleep Disturbance Short Form 8b (PROMIS SD SF 8b)

The PROMIS SF 8b will be filled out by the participants using the eDiary. All PROMIS SD SF 8b items must be answered to produce a valid total score. Missing data will not be imputed.

### 5.1.1.1.3 Menopause Specific Quality of Life Scale (MENQOL)

The MENQOL will be filled out by the participants using the eDiary.

For the MENQOL, participants have the option to skip single questions (e.g. if they do not feel comfortable to complete them). Missing item scores will be imputed, if the participant has responded to more than one half of the domain items (i.e. at least two items in the vasomotor domain, two items in the sexual domain, four items in the psychosocial domain items and nine items in the physical domain of the MENQOL). The imputed score is calculated from values converted for analysis according to scoring table ([Table 6–2](#)) and rounded to a whole number. The imputed value is the mean for that item generated from the other subjects who responded. For missing item score at baseline, all subjects who responded to the item are considered. For post-randomization, only the responses of the participants in the same treatment group are used. When data from other participants will be used for imputation half of the participants within a treatment group must have responded to the item before an imputed value can be calculated. If the participant answered ‘yes’ but did not indicate ‘how bothered’ she was (partially missing data), the value is imputed from her own answers by calculating the mean of her ‘bothered’ scores for all her ‘yes’ answers within that domain. If she answered ‘no’ to all other domain items, the imputed score would be generated from the mean of all the subjects who responded ‘yes’ to the same item as discussed above ([Lewis, 2004](#)). If missing item scores within a domain cannot be imputed (because participant responded to half or less than half of the domain items), the domain score will be set to missing and the total score will be calculated as the mean of the remaining available domains.

Further details of scoring are described in Section [6.2.3](#).

### 5.1.1.1.4 Sleepiness scale

The Sleepiness Scale will be assessed together with the HFDD evening diary at bedtime during selected time periods. It consists of three items asking the participant to rate the degree of sleepiness felt in the morning (item 1), afternoon (item 2) and evening (item 3).

Missing item level responses will not be imputed, the average of item scores will be used to create a daily sleepiness score. A 7-day average score can be derived if a daily sleepiness score is available for at least 5 out of 7 of days, otherwise the 7-day average score will be set as missing. The baseline value will be calculated by aggregating all available days during the 14 days prior to start of treatment to a mean daily sleepiness. A minimum of 11 days should be available for the derivation of the baseline value.

### 5.1.2 Data Rules

**Definition of baseline:** The latest available valid measurement excluding unscheduled measurements at or before the start of treatment (for treated subjects) / randomization date (for randomized but not treated subjects). If the last observation available prior to randomization is the measurement from the Screening Visit, this would be used as the baseline value. In case a wash-out period was necessary, measurements taken during the pre-screening visit will not be used as a baseline value unless specified otherwise.

**Change from baseline:** To calculate the absolute change from baseline the baseline value will be subtracted from the value under treatment/follow-up, i.e.,

$$\text{Absolute change} = \text{post baseline value} - \text{baseline value}.$$

Some parameters will be additionally analyzed as relative change defined as

$$\text{Relative change} = 100 * [(\text{post baseline value} - \text{baseline value}) / \text{baseline value}].$$

**Derivation of intercurrent event (ICE):** Intercurrent events that occurred from randomization day to day 84 inclusive will be flagged.

For the “permanent discontinuation of randomized drug” and “intake of prohibited medication having impact on efficacy”, if ICE occurs on or before the 5th day of the week, it will be flagged for the respective week. If the ICE occurs on the 6th or 7th day of the week, it will be flagged from the following week. For example, if the participant permanently discontinues from the randomized drug on the 2nd day of week 4, the ICE will be flagged from week 4 onwards. If the discontinuation from the randomized drug occurs on the 6th day of week 4, then the ICE will be flagged from Week 5 onwards. For the “intake of prohibited medication having impact on efficacy” ICE, if the end date for the impact on efficacy occurs on the 1st or 2nd day of the week, the respective week should not be flagged. If the end date of impact on efficacy occurs on or after the 3rd day of the week, the week should be flagged.

The “permanent discontinuation of randomized drug” ICE will be flagged for participants who were randomized but not treated. These participants have an event at randomization for the Kaplan-Meier analysis on the time from randomization to the first occurrence of the intercurrent event “Permanent discontinuation of randomized treatment”. For the main analytical approach, the missing post-baseline data will be imputed as described in Section 5.3.1.

**Derivation of post-treatment weeks for HFDD:** The post-treatment weeks, i.e. data collected after premature discontinuation of treatment, are counted from last treatment date +1 onwards. Post-treatment days of the week in which the discontinuation of randomized drug occurs will be included in the last treatment week and the first post-treatment week. For example, if a participant’s last dose intake was on day 39 (4th day of week 6), week 6 will include data from days 36-42 and the post-treatment week 1 will include the data from days 40-46. Data from post-treatment weeks are utilized in the model-based analyses, and shown in the listings, but not included in the descriptive tables.

**Laboratory values <X or >X:** For laboratory values lower than a limit of detection, which are given as <X, half the value of the X will be used for analysis (i.e., values reported as “<X”, “<X.X”, “<X.XX” or etc. the value for analysis used will be derived by “X/2”, “X.X/2”, “X.XX/2” etc.). Differences between 2 values <X will be assigned values of 0. Ratios between 2 values <X will be assigned a value of 1. For values which are higher than a limit of detection Y (given as >Y), the value of Y will be used for analysis.

**Repeated measurements at the same visit after start of treatment:** If more than one post-randomization measurement is available for a given visit, the first valid observation will be used in the data summaries and all observations will be presented in the data listings.

**Start of treatment** refers to the first drug intake and will be identified based on the eCRF entry.

**Time to event:** The randomization date will be used as the start date for the calculation of time to event. Therefore, the time of event will be defined as “date of event – randomization date +1”.

**Unscheduled Assessments:** Extra assessments (e.g. laboratory data or vital signs) associated with non-protocol visits will be included in listings, but not in the summary tables or figures, unless specified otherwise.

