**Questionnaires:** eC-SSRS = Electronic Columbia-Suicide Severity Rating Scale (participant rated), HFDD = Hot Flash Daily Diary, ISI = Insomnia Severity Index, MENQOL = Menopause Specific Quality of Life Scale, PROMIS SD SF 8b = Patient-reported Outcomes Measurement Information System Sleep Disturbance Short Form 8b

**a** If a participant discontinues prematurely from treatment after the baseline visit, an EoT visit will be performed as soon as possible. It will comprise the same assessments as the Week 52 visit, and should be scheduled at the latest within 14 days after the discontinuation of the study drug. If the participant in addition decides to withdraw from the study, the EoT Visit will be

followed after 4 weeks by the Follow-up Visit. If a participant discontinues from treatment but agrees to stay in the study, the next scheduled in person visit will cover the assessments expected to be performed during the FU visit, and therefore no FU visit is needed after T9. The handheld device will be collected at the last scheduled IP visit.

**b** during Week 23 & 24, Week 35 & 36 and Week 49 & 50

**c** Mammogram should be performed if the time that has elapsed since the previous mammogram is in line with local medical guidelines for the frequency of mammograms in the respective age group. In case a non-study mammogram was conducted during the time of study participation, the result should be documented. In this case the mammogram will not be done at Visit T9 or EoT.

**d** T9 only

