**Table 1–2 : Main Estimand: ICEs and Strategies to address them**

ICEs**	Reason for ICE	Strategy	Data handling method
Temporary Treatment interruption*	AEs (treatment related/unrelated)	Treatment policy	Utilise the collected data after ICE.
	COVID-19 and administrative reasons	Treatment policy	Utilise the collected data after ICE.
Permanent discontinuation of randomized treatment	AEs (treatment related/unrelated) or Lack of efficacy		
	For participants who remained untreated/on background therapy.	Treatment policy	Utilise the collected data after ICE.
	For participants who initiate alternative VMS treatment	Treatment policy	Utilise the collected data after ICE.
	Other treatment-unrelated reasons, including COVID-19	Treatment policy	Utilise the collected data after ICE.
Intake of prohibited concomitant medication having impact on efficacy	All reasons	Treatment policy	Utilise the collected data after ICE.

ICE = Intercurrent event, AE = Adverse event, VMS = Vasomotor symptoms

\*Definition of temporary treatment interruption:

Week 1 = Treatment taken on <5/7 days during week 1 (day 2-8).

Week 4 = Treatment taken <80% during weeks 1-4 (day 1-28) OR treatment taken on <5/7 days during either week 3 or 4 (days 15-28).

Week 8 = Treatment taken <80% during weeks 1-8 (day 1-56) OR treatment taken on <5/7 days during either week 7 or 8 (days 43-56).

[figure not shown]
Week 12 = Treatment taken <80% during weeks 1-12 (day 1-84) OR treatment taken on <5/7 days during either week 11 or 12 (days 70-84).

\*\*ICEs will be reviewed prior to the study unblinding

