**Table 5–2: Scheduled assessment weeks for ePROs**

Questionnaires	Assessment Week	Completion days (inclusive)
PROMIS SD SF 8b	1	8-9
PROMIS SD SF 8b	2	15-16
PROMIS SD SF 8b	3	22-23
PROMIS SD SF 8b, MENQOL	4	29-30
PROMIS SD SF 8b, MENQOL	8	55-57
PROMIS SD SF 8b, MENQOL	12	83-85

First, scheduled assessments during the completion days will be assigned to the respective week.

Only in case no scheduled assessment is available for a particular week, assessments done at EoT, unscheduled timepoints or follow-up (in this order of priority) will be used, and they will be mapped to the next available, protocol-planned assessment week as described below:

- If the assessment occurs during the completion days as above, it will be assigned to the respective week.
- Up to and including Week 3 (only PROMIS SD SF 8b): If the EoT/ follow-up/ unscheduled assessment is on 5th day of the week or later, then the assessment will be mapped to the respective week (i.e., assessments on Days 6-7\* will be mapped to Week 1, Days 12-14 to Week 2 and Days 19-21 to Week 3). Otherwise, no mapping will occur, and the respective week will be considered missing. If multiple assessments are available within a particular week, the last assessment (i.e., the one closest to the scheduled assessment) will be used for mapping.
- From Week 4 onwards: a 2-week window will be used to map the available assessments to Week 4 (Days 15-28), Week 8 (Days 43-54\*), or Week 12 (71-82\*). A similar 2-week window will be used for Week 18, Week 24, Week 36 and Week 52.

Within each 2-week-window, the last available assessment (i.e., the one closest to the scheduled assessment) will be used for mapping.

\*Week 1 = Days 2-8; Day 8 (week 1), Days 55/56 (week 8) and Days 83/84 (week 12) are scheduled assessments, and no mapping would be required, therefore, these days are not considered in the window for mapping.

- In case an assessment is assigned to Week 2 or 3 and to Week 4, based on the above rules, it will be shown for Week 2 or 3 in the descriptive tables.
- Assessments from follow-up visits will be shown as follow-up in the descriptive tables.

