- In the descriptive tables, data collected after premature discontinuation of treatment will not be shown for the respective treatment week. Assessments occurring up to 2 days after discontinuation (inclusive) will still be considered under treatment and shown for the respective week. Out of the assessment collected post treatment discontinuation (+ 2 days), the one closest to the planned time point of follow-up (i.e. discontinuation date + 28 days) will be shown as follow-up assessment. In case two assessments are equally close to that date, the first one will be selected.

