#### 5.3.1 Main Analytical Approach

The main estimand to answer the clinical question of the study is described in Section [1.1](#).

The frequency of moderate to severe HF and the change from baseline as well as the relative change (%) from baseline will be summarized using descriptive statistics (see Section [5.1](#)) by treatment group weekly until Week 12 and at Weeks 23, 24, 35, 36, 49 and 50 thereafter. The change from baseline over time in the frequency of moderate to severe HFs will be shown using line plots for means together with 95% CIs by treatment group.

Inference about the primary endpoints will be done based on a mixed model for repeated measures (MMRM). Prior to performing modeling with the MMRM, missing data will be handled in alignment with the estimand strategies for ICEs (described in Section [1.1](#)).

[Table 5–3](#) provides a detailed overview of the MMRM model for the change from baseline in frequency of HF.

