### 5.5 Exploratory Endpoints Analysis

The following exploratory endpoints will be analyzed by descriptive statistical methods as described in Section [5.1](#) by treatment group. The analysis will be based on the FAS. The ICEs will be handled according to the treatment policy. No missing data imputation is planned for the exploratory endpoints.

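### SAP 5.5 claims treatment policy for the exploratory endpoints, but SAP 5.1.2 keeps diary and MENQOL values after permanent discontinuation out of the weekly descriptive tables, the only analysis most of them have

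*SAP*

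**What the plan says.** SAP 5.5 analyses the exploratory endpoints descriptively on the FAS, without imputation, and states: "The ICEs will be handled according to the treatment policy". The SAP makes clear what that means. In Table 1–2 every row, including permanent discontinuation, carries the handling "Utilise the collected data after ICE", and SAP 5.3.1 describes the policy as using everything collected whether or not an intercurrent event occurred.

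SAP 5.1.2 sets a different rule for the tables. For the diary (HFDD), after permanent discontinuation: "Data from post-treatment weeks are utilized in the model-based analyses, and shown in the listings, but not included in the descriptive tables". The remaining days of the week in which drug stops still count in the last treatment week. For PROMIS and MENQOL: "In the descriptive tables, data collected after premature discontinuation of treatment will not be shown for the respective treatment week". Two exceptions apply: assessments up to 2 days after stopping count as on treatment, and of the later ones "the one closest to the planned time point of follow-up (i.e. discontinuation date + 28 days) will be shown as follow-up assessment".

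The only model for a diary variable is the MMRM in Table 5–3, on moderate-to-severe hot flash frequency at Weeks 1, 4, 8 and 12. SAP 5.1.2 flags intercurrent events only up to Day 84. Protocol 7.1 asks women who stop drug to stay in the study until Visit T9, so such data are meant to exist.

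**The concern.** A reader of 5.5 would expect the exploratory FAS tables to include women who stopped drug and kept reporting. Under 5.1.2 they do not: the later-week means come from women still on drug, a group formed after randomisation. The sentence that sends post-treatment diary weeks to the model-based analyses offers no remedy where no model exists. At stake is how the 52-week course of these endpoints is read, since after Week 12 the descriptive displays are the only efficacy summaries of the diary. The exclusion also names tables only, so the SAP does not say which rule the line plots and proportion graphs follow.

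**Working it through.** **Which endpoints are affected.** SAP 5.5 lists eight exploratory endpoints. Two (body weight, body composition) fall outside the diary and questionnaire rules. The other six are moderate-to-severe frequency, severity, frequency of all hot flashes, night-time awakenings, sleep disturbance, and MENQOL domains and items. Only moderate-to-severe frequency has a model, at four visits up to Week 12. So 5 of 6 have none, and no diary endpoint has one at Weeks 23 to 50.

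**One woman, last dose Day 60, all later assessments completed.**
- Diary summaries are scheduled "weekly until Week 12 and at Weeks 23, 24, 35, 36, 49 and 50 thereafter": 12 + 6 = 18 weeks. Week 9 (Days 57–63) stays. Weeks 10, 11, 12, 23, 24, 35, 36, 49 and 50 leave the tables: 9 of 18. Only her Week 12 moderate-to-severe frequency re-enters, through the MMRM.
- MENQOL: the 2-day grace ends on Day 62. The follow-up target is Day 60 + 28 = 88. Her on-schedule Week 12 value (Days 83–85) is 5 to 3 days from it; an end-of-treatment value (at latest Day 60 + 14 = 74) is at least 14 days away. The Week 12 value therefore appears as follow-up, unless a nearer one exists, and not under Week 12. Her Week 24, 36 and 52 values appear in no descriptive table. The same holds for Week 18, which the protocol's schedule marks for MENQOL although SAP 6.2.3 does not list it.

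**How many women.** The planning figures in SAP 3 reproduce: 300 × 0.9 = 270 (Week 12 power), 300 × 0.8 = 240 (6 months), 300 × 0.7 = 210 (1 year). The power table also reproduces (77.1%, 98.2%, >99.9%) and is not touched by this point. Permanent discontinuations by about Day 84: at most 300 − 270 = 30. This is an upper bound, because drop-outs need not give later data.

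**Size.** Let s be the number of these early stoppers giving data at a visit and m the number still on drug (270, 240, 210). Their weight among women with data is w = s/(m + s). Later stoppers are left out on both sides.

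- Shift in an arm mean = w × g, where g is the stayer-minus-stopper gap in mean change.
- Excess of the on-treatment difference over the all-data difference, with equal stopping in both arms and a share r of the benefit kept: 1/(1 − w(1 − r)) − 1.

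| | Week 12 | Week 24 | One year |
|---|---|---|---|
| w, all 30 give data | 30/300 = 10% | 30/270 = 11.1% | 30/240 = 12.5% |
| Excess, all give data, r = 0 | 11.1% | 12.5% | 14.3% |
| Excess, half (15) give data, r = 0 | 5.6% | 6.2% | 7.1% |
| Excess, all give data, r = 0.5 | 5.3% | 5.9% | 6.7% |
| Excess, none give data | 0% | 0% | 0% |

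For all-hot-flash frequency, an assumed g of 1 to 3 per day moves an arm mean by 0.10–0.30 at Week 12 and 0.125–0.375 at one year if all 30 report.

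If stopping differs between arms and g is the same in both, the Week 12 difference moves by g × (d_E − d_P), where d_E and d_P are the shares stopped on elinzanetant and placebo. With 10% on elinzanetant against 5% or 15% on placebo this is +0.05g or −0.05g, so the direction is open. Placebo stopping, the share giving data, r and g are all assumptions; the documents give none of them.

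**The case against.** The strongest reply is that 5.5 itself refers to Section 5.1 for its methods, and the exclusion sits there, stated explicitly and with a worked example for the diary. A programmer would have no doubt which rule to apply. That stands, but it settles only what will be produced. The output will still not be what the treatment policy sentence in 5.5 says.

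On-treatment descriptive summaries are also a legitimate choice for exploratory endpoints. The SAP already reports non-missing n (5.1), intercurrent events by week and arm, and Kaplan-Meier plots of discontinuation (5.2), with post-treatment diary weeks listed. That lowers the weight of the point. It does not supply a summary that includes these women.

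The sample size section uses the 10% drop-out to cut N to 270 at Week 12, as if those women gave no Week 12 value. If so, there is nothing to add back and the effect is zero. This also stands.

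On figures, the SAP introduction places table, figure and listing specifications in a separate document. The silence about plots is therefore a gap in the SAP, not a shown inconsistency.

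A reader might infer much larger distortions by counting every planned stopper: 300/240 − 1 = 25% at Week 24 and 300/210 − 1 = 43% at one year. The documents do not support this. Events are flagged only to Day 84, so the treatment policy sentence has no formal application to later stops. Nor is any between-arm difference planned for these endpoints, so no planned estimate is overstated by any percentage.

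**Conclusion.** The inconsistency is real and limited. For five of the six diary and MENQOL endpoints in 5.5, the stated treatment policy strategy is not carried out for permanent discontinuation by Day 84. Moderate-to-severe frequency is covered only at the four modelled visits. At most about 30 of 300 elinzanetant women are concerned on the planning rate. The 11%, 12.5% and 14% figures are worst-case illustrations for a reader who subtracts arm means, not forecasts.

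Two broader readings should be resisted. One is that the primary result is affected: the MMRM uses post-treatment data, so it is not. The other is that the contradiction covers PROMIS, the MENQOL total score, the subgroup tables and later stops. SAP 5.4 and 5.7.2 make no treatment policy claim, so those need only a clear label. Temporary interruption and prohibited medication are not affected, since 5.1.2 excludes nothing after them. Weight: minor, to something that should be fixed.

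**What to change.** For the diary and MENQOL endpoints in 5.5, add FAS tables that summarise all collected data at the scheduled study week, including after discontinuation, with n on and off drug per week and arm.

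A mapping rule is needed for visits that serve two purposes. Footnote a to Table 1–2 of the protocol says that for a woman who stops drug but stays in, "the next scheduled in person visit will cover the assessments expected to be performed during the FU visit", while SAP 5.1.2 says "Assessments from follow-up visits will be shown as follow-up in the descriptive tables". In the new tables such a value should count at its scheduled week; it should appear as follow-up only in the existing tables. Keep the existing tables, titled 'on-treatment observed-case', and state that each line plot and proportion graph follows the rule of the table it accompanies.

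At minimum, amend 5.5 to say that data after permanent discontinuation are excluded from the weekly descriptive tables (a while-on-treatment strategy for that event), and title all tables built on 5.1.2 accordingly, including the secondary and subgroup tables.

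Cost: SAP wording, one mapping rule and a further run of existing programs on data already collected; power and sample size do not change. The downside is extra output, fewer follow-up values in the new tables for women whose visit doubles as follow-up, and long-term means that may look less favourable. The minimum version costs wording and titles only.

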### **8.2.2 Vital Signs**

- Pulse rate, and systolic and diastolic blood pressure will be assessed.
- Vital signs measurements should be preceded by at least 5 minutes of rest for the participant in a quiet setting without distractions (e.g., television, cell phones).
- Vital signs should be taken before blood collection for laboratory tests.
- Blood pressure and pulse rate measurements will be assessed once in a sitting position with a completely automated device. Manual techniques will be used only if an automated device is not available.

- In case of abnormal results, repeat measurements should be performed to adequately document potential findings, e.g. hypertension.

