#### 5.6.3.2 Vital signs

Vital signs (pulse rate, systolic blood pressure and diastolic blood pressure) will be summarized by treatment group for each visit, including change from baseline where appropriate, using descriptive statistics as described in Section 5.1. The absolute values by visit and by treatment group will be shown using boxplots. In addition, for systolic and diastolic blood pressure the line-plots depicting the mean change from baseline  $\pm 95\%$  CI by treatment group as well as scatter plot (with regression lines) showing blood pressure values at Week 12 and end of treatment (EoT) against baseline by treatment group will be provided.

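### For repeat readings the SAP uses the latest value at baseline but the first value at later visits; if blood-pressure repeats are stored under the baseline visit, by-arm mean change is shifted slightly upward

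*SAP*

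**What the plan says.** Four places bear on the point.

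- **Baseline (SAP 5.1.2).** Baseline is "The latest available valid measurement excluding unscheduled measurements at or before the start of treatment (for treated subjects"; for women randomized but never treated, the reference date is randomization. For change from baseline, "the baseline value will be subtracted from the value under treatment/follow-up", so a lower baseline gives a larger change.
- **After baseline (SAP 5.1.2, the entry on repeats within a visit once dosing has begun).** The rule reads: "If more than one post-randomization measurement is available for a given visit, the first valid observation will be used in the data summaries". By its heading and wording this rule does not reach readings taken before the first dose.
- **When repeats occur (Protocol 8.2.2).** "Blood pressure and pulse rate measurements will be assessed once in a sitting position with a completely automated device". Then: "In case of abnormal results, repeat measurements should be performed to adequately document potential findings, e.g. hypertension". Repeats are therefore selective, made because the first value was abnormal.
- **What is reported (SAP 5.6.3.2).** Pulse rate and blood pressure are summarized by arm and visit with change from baseline. In addition, "for systolic and diastolic blood pressure the line-plots depicting the mean change from baseline" with 95% confidence intervals are planned, as are scatter plots of Week 12 and end-of-treatment values against baseline. The section has no rule of its own for choosing or averaging readings.

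The SAP 5.1.2 entry on unscheduled assessments covers extra assessments, vital signs included, that belong to visits outside the protocol schedule. It sends them to listings only.

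**The concern.** The two selection rules differ, and the repeat process is one-sided when high readings are the ones that prompt a repeat. At baseline a high first reading gives way to the later one, which is lower on average by regression to the mean. After baseline the high first reading is kept. A woman who reads 134 then 127 at both visits is scored 134 − 127 = +7 mmHg although nothing changed.

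Every later visit is compared with the same baseline, so the shift would appear at the first post-baseline visit and persist. On the planned line plots it would look like a small sustained rise in each arm. What is at stake is how those within-arm safety displays are read. No test or efficacy result is affected.

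**Working it through.** **Is a baseline repeat eligible?** The baseline rule excludes unscheduled measurements. The only description of extra assessments in SAP 5.1.2 ties them to non-protocol visits. The baseline visit is a protocol visit with vital signs in the Schedule of Activities, so on that wording a second reading there is not clearly excluded. The SAP does not say how it is coded.

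**Are baseline repeats plausible?** Protocol 5.2, exclusion criterion 5, admits women with mild hypertension if medically cleared, with screening pressure up to 139/89. The footnote defines hypertension from 130/80. Some women will have high readings at baseline.

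**Inputs.** The documents state no blood-pressure figure to reproduce, and no mean, variance or numeric repeat trigger. Everything below is assumed:

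- SBP: mean 122, between-woman SD 11, visit-to-visit SD 6, within-visit reading SD 3, 5 or 8 mmHg.
- DBP: mean 77, between-woman SD 7, visit-to-visit SD 4, within-visit SD 2, 4 or 6 mmHg.
- Repeat threshold 130 or 140 (SBP), 80 or 90 (DBP), applied to each pressure separately.

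**Closed form.** Let sw be the within-visit SD, st the total SD of one reading, T the threshold, mu the mean and φ the standard normal density. With no true change, every reading at or above T repeated and no eligibility cut:

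shift = (sw² / st) × φ((T − mu) / st)

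For SBP with sw = 5 and T = 130:

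- st = √(11² + 6² + 5²) = √182 = 13.49
- (130 − 122) / 13.49 = 0.593
- shift = (25 / 13.49) × φ(0.593) = +0.62 mmHg

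The same formula gives +0.23 for sw = 3 and +1.49 for sw = 8. With T = 140 and sw = 5 it gives +0.30. Simulation without the eligibility cut agrees: +0.24, +0.63 and +1.48 at T = 130, and +0.30 at T = 140.

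**Simulation with a screening cut** (SBP ≤ 139 or DBP ≤ 89; 4 million women per scenario before the cut; all high readings repeated; no true change):

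| | Threshold | Low SD | Middle SD | High SD |
|---|---|---|---|---|
| SBP (within-visit SD 3, 5, 8) | 130 | +0.23 | +0.61 | +1.44 |
| SBP (within-visit SD 3, 5, 8) | 140 | +0.08 | +0.24 | +0.68 |
| DBP (within-visit SD 2, 4, 6) | 80 | +0.19 | +0.68 | +1.37 |
| DBP (within-visit SD 2, 4, 6) | 90 | +0.04 | +0.20 | +0.52 |

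At the 130 threshold, 21% to 24% of women had a baseline repeat.

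**Sensitivity** (SBP, threshold 130, with the cut):

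- Half of high readings repeated, SD 5: +0.30 instead of +0.61.
- Readings below 100 also repeated, SD 5: +0.39.
- Mean 126 instead of 122, SD 8: +1.65.

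A second set of assumptions (SBP mean 120–124, between-woman SD 11–12, within-visit SD 4–8; DBP mean 77, SD 7.5, reading SD 0.65 times that of SBP; triggers 130/80 or 140/90) gave about +0.1 to +1.1 mmHg SBP and +0.05 to +0.9 mmHg DBP.

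**One rule on both sides.** First reading at both times, or last reading at both times, gave 0 within simulation error (largest absolute value about 0.02). The mean of all readings at both times also has zero expected shift, because with no true change the two visits then have the same distribution.

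**Scale.** With 300 women per arm and an assumed SD of change of 10 to 12 mmHg, the per-arm 95% interval half-width is 1.96 × 10/√300 = 1.1 to 1.96 × 12/√300 = 1.4 mmHg.

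**The case against.** The strongest reply is that the effect may never occur. Blood pressure is planned once per visit, so a repeat could be coded as unscheduled. The baseline rule would then drop it, fall back to the scheduled reading, and the shift would vanish. The entry on extra assessments governs what goes into tables and is not labelled as a definition for the baseline rule. This stands: the effect is conditional, and what the documents establish is an unstated classification combined with two different rules. A related reply is that latest may refer to the visit and not to the reading. In that case the SAP has no rule for two readings at the baseline visit, and the same clarification is needed.

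A reader might take 130/80 as the protocol's repeat trigger. It is not. It is the footnote definition of hypertension, which requires three readings on at least two occasions; Protocol 8.2.2 speaks only of abnormal results. How often sites repeat, and at what level, is unknown, and some repeats may fall at non-protocol visits that the SAP excludes anyway.

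A reader might also infer that a drug effect on blood pressure would be created or hidden. The documents do not support that. Randomized arms share the same baseline process, so the shift is equal in expectation in both arms. The safety analyses are descriptive, no blood-pressure hypothesis is tested, and the placebo curve would show the same rise.

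**Conclusion.** The asymmetry between the two rules is in the current text, the protocol makes repeats selective, and SAP 5.6.3.2 does not override either rule. If same-visit repeats are held under the baseline visit, by-arm mean blood-pressure change and the plots against baseline are shifted slightly upward in both arms with no true change. If they are coded as unscheduled, there is no shift. It cannot be said from the documents that the shift will occur, and the between-arm contrast is unbiased either way.

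The size is illustrative: roughly 0.05 to 1.5 mmHg for assumed within-visit SDs of 2 to 8 mmHg and triggers of 130/80 or 140/90, slightly more with a higher assumed mean, and less with incomplete repeats or repeats of low readings. Against an assumed per-arm interval half-width of 1.1 to 1.4 mmHg, that runs from negligible to about the full half-width. The point is minor, but cheap to settle.

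**What to change.** Add to SAP 5.6.3.2, for vital signs only:

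- One within-visit rule applies at baseline and at every later visit: either the first valid reading or the mean of all valid readings at that visit.
- Repeat readings at a protocol visit, including baseline, are handled by that rule and are not treated as unscheduled.
- All readings remain in the listings.

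The general baseline definition in SAP 5.1.2 should stay as it is. Changing it would alter baseline selection for laboratory values and other parameters that this point does not concern.

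The cost is a few lines of text, one extra derivation step in the vital-signs program, and a small departure from the general baseline rule. No new data are needed and no clinic procedure changes.
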